7.3.7. Suicidal Risk Monitoring

GSK2982772 is considered to be a CNS-active drug. There has been some concern that some CNS-active drugs may be associated with an increased risk of suicidal thinking or behaviour when given to some patients with PsO. Although this drug has not been shown to be associated with an increased risk of suicidal thinking or behaviour when given to healthy volunteers, GSK considers it important to monitor for such events before or during clinical studies with compounds such as this.

Families and caregivers of subjects being treated with GSK2982772 should be alerted about the need to monitor subjects for the emergence of unusual changes in behaviour, as well as the emergence of suicidal ideation and behaviour and to report such symptoms immediately to the study investigator.

Subjects being treated with GSK2982772 should be monitored appropriately for suicidal ideation and behaviour or any other unusual changes in behaviour. All subjects who experience signs of suicidal ideation or behaviour must immediately be discontinued from study medication.

At Screening and baseline (pre-dose Day 1), the 'Baseline/Screening CSSRS' (Columbia Suicide Severity Rating Scale) will be completed. At Days 43 (week 6) and Day 85 (week 12), the 'Since Last Visit CSSRS' will be completed. GSK Version 4.1 of both rating scales will be used.

Subjects who answer 'yes' to any suicidal behaviour or 'yes' to suicidal ideation Questions 4 or 5 will be referred to their GP or appropriate psychiatric care. The medical monitor will be notified. If appropriate, an AE or SAE should be reported (see Section 7.3.1 - AE and SAE). In addition, the investigator should complete a Possible Suicidality Related Adverse Event (PSRAE) form to collect detailed information on the circumstances of the reported AEs which, in the investigator's opinion, are possibly suicidality-related. These may include, but are not limited to, an event involving suicidal ideation, a preparatory act toward imminent suicidal behaviour, a suicide attempt, or a completed suicide.

7.4. Efficacy

7.4.1. Patient Reported Outcomes

Note: Patient Reported Outcomes questionnaires should be completed by subjects before any other assessments at a clinic visit.

7.4.1.1. Itch Visual Analogue Scale

The subject will be asked to rate the intensity of itch over the past week by marking a line on a 10 cm VAS with anchors “0” (no noticeable itching) to “10” (maximum itching sensation).

7.4.1.2. Dermatology Life Quality Index

The DLQI [Finlay, 1994] will be used to assess quality of life. The subject will complete the questionnaire to evaluate how their psoriasis has affected their life over the previous week before the assessment occurs. Each question will be scored out of 0-3 or 0-2, as follows.

- 0 = Not at all
- 1 = A little
- 2 = A lot
- 3 = Very much

The questionnaire comprises of 10 questions (see SRM for full details).

7.4.2. Clinical Disease Assessments

7.4.2.1. Body Surface Area (BSA)

The BSA affected with psoriasis will be evaluated at Screening and baseline (pre-dose Day 1) and on Day 85 by the investigator or suitably trained delegate. In order to be eligible for the study, BSA must be $\geq 3\%$. As a reference, the area of the whole palm is counted as 1% BSA.

7.4.2.2. Selection of Psoriasis Plaques and Plaque Lesion Severity Scoring (PLSS)

Two plaques of at least 3 cm by 3 cm in area will be selected during the Screening period, one for clinical assessment (clinical efficacy skin lesion) and one for skin biopsy (punch biopsies). If at baseline on Day 1, prior to dosing, another lesion appears more suitable, the selected lesion can be changed. Once the lesions have been selected at baseline on Day 1, they must not change.

At a minimum, each plaque will have an induration score of ≥ 2 (moderate or above) and a score of ≥ 1 in erythema and scaling. The PLSS is the sum of the erythema, scaling and plaque thickness scores. Each lesion must have a PLSS score of ≥ 5 .

Ideally, the biopsy skin lesion should be the most severe plaque of the two.

Selected lesions should be located on areas (trunk or extremities) that can be shielded to reduce natural exposure to UV light and should not include scalp, inguinal, genital lesions, or the palmar surfaces of the hands and/or feet. Preferably, symmetrical lesions will be chosen, but this is not an absolute requirement.

During the study, the PLSS will be recorded for the clinical efficacy skin lesion (the biopsy lesion is only for biopsy).

7.4.2.3. Psoriasis Area Severity Index (PASI)

The PASI scoring system is a widely-used standard clinical tool for assessing the severity of psoriasis that takes into account the overall severity of erythema (redness), thickness (induration), and scaling, as well as the extent of BSA affected with psoriasis [Fredriksson, 1978]. Erythema, induration, and scale are each graded on a 5-point scale (0-4), and the % BSA affected is scored on a 7-point scale (0-6) for each of the 4 specified body regions (head, upper extremities, trunk, and lower extremities). The body region scores are each multiplied by a weighted factor; and the sum of the region scores give the overall PASI score. Higher scores indicate more severe disease. PASI is a static measurement made without reference to a previous score (see SRM for full details).

The PASI assessment will be performed by the investigator or suitably trained delegate, and whenever possible, the PASI assessments for an individual subject will be completed by the same assessor at all time points.

7.4.2.4. Digital Photography

Photographs will be taken by the investigator or designee to illustrate any visible changes in psoriasis target lesions selected on Day 1. For each subject, the investigator or delegate will take photographs of the same area of the body at each time point (i.e., same background, same illuminations, and same distance from the body). Photographs will be taken of the area(s) of the body where the selected lesions are present and should be taken prior to performing the biopsy. Photographs of the face will not be taken. Photographs will be stored electronically, labelled, and collected centrally as explained in the Image Acquisition Guidelines. Photographs will be used to document visual changes in lesions. Date, time and location of the photographs will be captured in the CRF.

Further details are contained in the Image Acquisition Guidelines.

7.4.2.5. Physician's Global Assessment of Disease Activity

The investigator or physician designee only will complete a global assessment of disease activity using the physician global assessment item. A 6-point scoring system will be used to measure the severity of psoriatic lesions over the entire body at the time of evaluation (see SRM for full details).

Note:

- The investigator or physician designee should complete the physician's global assessment independently of the subject.
- Ideally, the same investigator or physician designee should perform all global assessments for each subject for the duration of the study.

7.5. Pharmacokinetics

7.5.1. Blood Sample Collection

Blood samples for pharmacokinetic (PK) analysis of GSK2982772 will be collected at the time points indicated in Section 7.1, Time and Events Table. The actual date and time of each blood sample collection will be recorded. The timing of PK samples may be altered and/or PK samples may be obtained at additional time points to ensure thorough PK monitoring.

Details of blood sample collection, processing, storage and shipping procedures are provided in the laboratory manual.

7.5.2. Sample Analysis

Plasma analysis will be performed at a bioanalytical site (to be detailed in the SRM) under the control of Platform Technologies and Science In vitro/ In vivo Translation (PTS IVIVT) and Third Party Resource, GlaxoSmithKline. Concentrations of GSK2982772 will be determined in plasma samples using the currently approved bioanalytical methodology. Raw data will be archived at the bioanalytical site (detailed in the SRM). Once the plasma has been analyzed for GSK2982772 any remaining plasma may be analyzed for other compound-related material and the results reported under a separate PTS-IVIVT, GlaxoSmithKline protocol.

7.5.3. Punch Skin Biopsy for Pharmacokinetic Assay

See Section 7.6.1 for more details on punch skin biopsies. A punch skin biopsy will be taken at baseline (pre-dose Day 1) and Day 43 (Week 6) to measure the concentration of GSK2982772 in the skin (taken from the outer third of the target lesion). Information on processing the biopsies for the skin pharmacokinetic assay will be provided in the SRM.

Once the skin extract has been analyzed for GSK2982772, any remaining skin extract may be analyzed for other compound-related material and the results reported under a separate PTS-IVIVT, GlaxoSmithKline protocol.

7.5.4. Sample Analysis

Skin biopsy sample analysis will be performed under the control of PTS-IVIVT, GlaxoSmithKline. An exploratory analysis of concentrations of GSK2982772 in skin will be conducted.

7.6. Biomarker(s)/Pharmacodynamic Markers

7.6.1. Skin Lesion Biopsy

At baseline (pre-dose Day 1), a target lesion for biopsy will be identified (≥ 3 cm by 3 cm) on the trunk or extremities. The same target lesion will be used for both the baseline lesion biopsy and at Day 43 (Week 6) even if the lesion has cleared. Lesions on palmar

surfaces of the hands and feet, scalp, knees, elbows and intertriginous areas will not be used as the target lesion site.

- Two 4-mm tissue biopsies will be taken from the outer third of the selected biopsy lesion at baseline (pre-dose Day 1) using standard methodology. The second site on the outer third of the same lesion should be at least 1.5 cm from the first biopsy. Local anaesthetic will be administered before each biopsy, and only suitably experienced personnel, trained in aseptic technique, will obtain the biopsies.
- At baseline only (pre-dose Day 1), a total of 3 biopsies will be taken, 1 from a non-lesional area of skin and 2 biopsies will be taken from the target lesion site. The target lesion biopsy will be taken from the outer third of the lesion. The non-lesional biopsy will be taken from an unaffected area close to the target lesion, and cannot include the palmar surfaces of the hands and feet, scalp, knees, elbows and intertriginous areas
- At Day 43 (Week 6), 2 biopsies will be taken from the same target lesion as identified at baseline even if the lesion has cleared. As above, the biopsies will be taken from the outer third of the lesion.

Biopsy tissue taken from the psoriatic skin lesions will be divided accordingly for pharmacokinetic, target and pathway engagement, histological and gene expression analyses as feasibility dictates. Histologic assessment will include measurement of epidermal thickness, total inflammatory infiltrates, keratin expression (e.g., K16) and specific cell numbers (which may include by not be limited to) CD3+T-cells, CD11c+ myeloid dendritic cells. mRNA may be isolated from skin biopsy tissue, as feasibility dictates, to determine the effect of placebo and GSK2982772 on markers of inflammation and tissue healing (e.g., may include and not be limited to measurement of chemokines, cytokines, and extracellular matrix proteases). Examples of technologies that may be used for analysis include, but are not limited to quantitative PCR, RNAseq, microarray, mass cytometry (CyTOF). See SRM for full details of the division of biopsy tissues.

The baseline nonlesional skin biopsy will be divided accordingly for histologic and gene expression analysis as feasibility dictates. Histologic assessment will include measurement of epidermal thickness, total inflammatory infiltrates, keratin expression (e.g., K16) and specific cell numbers (which may include by not be limited to) CD3+T-cells, CD11c+ myeloid dendritic cells. mRNA expression of inflammatory markers and tissue healing will be assessed in baseline nonlesional skin (as above) as feasibility dictates, using the same technologies as outlined above.

7.6.2. Novel Pharmacodynamic Biomarkers

7.6.2.1. RIP1 Target Engagement in Blood

Blood samples for RIP1 target engagement will be collected at the time points indicated in Section 7.1 to measure levels of free and total RIP1 antibodies.

7.6.2.2. RIP1 Target Engagement in Tissue

Skin punch biopsy samples for RIP1 target engagement will be collected at the time points indicated in Section 7.1 to measure levels of free and drug-bound RIP1 protein if sample quantity and data allow.

7.6.2.3. RIP1 Pathway Markers in Tissue

Skin punch biopsy samples for RIP1 pathway markers will be collected at the time points indicated in Section 7.1 to measure total or phosphorylated RIP1, RIP3, MLKL and cleaved or total caspase 3 and 8 if sample quantity and data allow.

7.6.3. Exploratory Novel Biomarkers

With the subject's consent, tissue, and/or blood sample(s) will be collected during this study and may be used for the purposes of measuring novel biomarkers to identify factors that may influence disease/condition for study treatment, and/or medically related conditions, as well as the biological and clinical responses to GSK2982772. If relevant, this approach will be extended to include the identification of biomarkers associated with adverse events.

Samples will be collected at the time points indicated in Section 7.1. The timing of the collections may be adjusted on the basis of emerging pharmacokinetic or PD data from this study or other new information in order to ensure optimal evaluation of the PD endpoints.

Novel candidate biomarkers and subsequently discovered biomarkers of the biological response associated with PsO and/or the action of GSK2982772 may be identified by application of:

- Gene expression array analysis may be conducted on the blood and/or punch skin biopsies using microarray, and/or alternative equivalent technologies such as RNA sequencing, which facilitates the simultaneous measurement (and confirmation) of the relative abundances of thousands of RNA species resulting in a transcriptome profile for each skin sample.
- Soluble inflammatory mediators in the blood may be assayed for cytokine and inflammatory mediators including, but not limited to, pro-inflammatory and anti-inflammatory cytokines, chemokines, and acute phase proteins.
- Phosphoprotein detection in skin tissue and blood may be used to validate RIP1 kinase pathway activation.
- High dimensional CyTOF/Helios based immune profiling of peripheral blood cells including measurement of immune cell phenotypes, intracellular signalling events and key cytokines / chemokines.

These analyses may be reported under separate protocol following the completion of the study. All samples will be retained for a maximum of 15 years after the last subject completes the trial.

7.7. Genetics

In consenting subjects, a blood sample for pharmacogenetics (PGx) research will be drawn on Day 1 (or any time point post randomisation and prior to study completion) to better characterize genetic variability that may affect efficacy or safety endpoints. Information regarding pharmacogenetic (PGx) research is included in [Appendix 3](#).

8. DATA MANAGEMENT

- For this study subject data will be entered into GSK defined CRFs, transmitted electronically to GSK or designee and combined with data provided from other sources in a validated data system.
- Management of clinical data will be performed in accordance with applicable GSK standards and data cleaning procedures to ensure the integrity of the data, e.g., removing errors and inconsistencies in the data.
- Adverse events and concomitant medications terms will be coded using MedDRA (Medical Dictionary for Regulatory Activities) and an internal validated medication dictionary, GSKDrug.
- CRFs (including queries and audit trails) will be retained by GSK, and copies will be sent to the investigator to maintain as the investigator copy. Subject initials will not be collected or transmitted to GSK according to GSK policy.

9. STATISTICAL CONSIDERATIONS AND DATA ANALYSES

9.1. Hypotheses

The primary objective of the study is to investigate the safety and tolerability of GSK2982772 60 mg BID and 60 mg TID following 12 weeks of treatment. No formal statistical hypotheses will be conducted to assess this objective.

If appropriate, comparisons between the GSK2982772 arms and the placebo arm will be made to investigate the secondary inflammatory, mechanistic and efficacy objectives. Trends over time will be investigated for both treatment arms along with associations between each of the parameters.

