16. History of alcohol or drug abuse that would interfere with the ability to comply with the study.
17. Subject intends to sunbathe or use a tanning device (sun bed or solarium) within 14 days prior to Day 1 and until completion of the follow up visit (Day 112).

CONTRAINDICATIONS

18. History of sensitivity to any of the study treatments, or components thereof or a history of drug or other allergy that, in the opinion of the investigator or Medical Monitor, contraindicates their participation.
19. Received a live or attenuated vaccine within 30 days of randomization OR plan to receive a vaccination during the study until completion of the follow-up visit.
20. The subject has participated in a clinical trial and has received an investigational product within 30 days or 5 half-lives, whichever is longer before the first dose of study medication, or plans to take part in another clinical trial at the same time as participating in this clinical trial. Subjects who were randomized into Cohort 1 are not eligible to be re-randomized into Cohort 2.

DIAGNOSTIC ASSESSMENTS AND OTHER CRITERIA
21. Haemoglobin <11 g/dL; haematocrit <30%, white blood cell count \leq 3000/mm ³ (\leq 3.0 x 10 ⁹ /L); platelet count \leq 100,000/ μ L (\leq 100 x 10 ⁹ /L); absolute neutrophil count \leq 1.5 x 10 ⁹ /L at the screening visit.
22. Presence of hepatitis B surface antigen (HBsAg), positive hepatitis C antibody test result at screening or within 3 months prior to first dose of study treatment. As potential for and magnitude of immunosuppression with this compound is unknown, subjects with presence of hepatitis B core antibody (HBcAb) should be excluded. Subjects positive for HBsAg and/or positive for anti-HBc antibody (regardless of anti-HBs antibody status) are excluded.
23. A positive serology for human immunodeficiency virus (HIV) 1 or 2 at screening.
24. Where participation in the study would result in donation of blood or blood products in excess of 500 mL within 3 months.
25. Exposure to more than 4 investigational medicinal products within 12 months prior to the first dosing day.

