6.2. Treatment Assignment

At screening, a unique Subject Number will be assigned to any subject who has at least one Screening procedure performed, other than informed consent. The unique Subject Number will be used to identify individual subjects during the course of the study.

Subjects who meet screening eligibility criteria will be randomised to a treatment group through Interactive Response Technology System (IRTS). The IRTS will confirm the subject's CRF number (Subject Number) and provide the randomisation number, where:

- A randomisation number will be assigned from a randomisation schedule generated by Clinical Statistics, prior to the start of the study, using validated internal software. Once assigned, this number must not be reassigned to any other subject in the study.

The randomisation is centrally controlled by the IRTS.

In Cohort 1, subjects will take study medication every day, twice a day, approximately 12 hours apart. Subjects will be randomised to receive either GSK2982772 or placebo in a 2:1 ratio. In Cohort 2, subjects will take study medication every day, three times a day, with approximately 8 hours between each dose. Subjects will be randomised to receive either GSK2982772 or placebo in a 3:1 ratio.

Subjects will be administered the first daily dose of study medication by site staff during the site visit for Day 1 (week 0) and Day 43 (week 6). Subjects will self-administer all other doses of study medication and will record the date and time in the diary cards provided to them.

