9.2. Sample Size Considerations

9.2.1. Sample Size Assumptions

[figure not shown]
The study is not powered to detect pre-defined differences. In Cohort 1, approximately 30 subjects and up to a maximum of 36, will be randomised into the study to either GSK2982772 or placebo in a 2:1 ratio to ensure that approximately 24 evaluable subjects complete the study.

In Cohort 2, approximately 24 subjects and up to a maximum of 32, will be randomised into the study to either GSK2982772 or placebo in a 3:1 ratio to ensure that approximately 20 evaluable subjects complete the study.

A subject is considered evaluable if they have completed at least one post-treatment biopsy.

The primary objective of the study is safety and tolerability, where there will be 20 subjects randomised to GSK2982772 60 mg BID and 18 subjects randomised to GSK2982772 60 mg TID. Using a Bayesian approach to determine the confidence interval around an observed safety event, we would assume a flat Beta (1, 1) prior, and if we were to observe one safety event in 20 then the posterior distribution would be Beta (2, 20), as outlined below in [Figure 4](#).

Figure 4 One Event in 20 Subjects: Beta (2,20) Distribution

Thus, we can be 95% certain that the true probability of the safety event lies between 0.01 and 0.24. Similarly, if we were to observe one safety event in 18 then the posterior

distribution would be Beta (2, 18), thus we can be 95% certain that the true probability of the safety event lies between 0.01 and 0.26.

For supportive information the properties of the secondary endpoint PLSS have also been considered. Assuming a standard deviation of 25%, it is estimated that the lower and upper bounds of the 95% confidence interval for the difference between GSK2982772 60 mg BID (n=20) and placebo (n=10) in percentage change in index lesion PLSS will be within approximately 17.1% of the point estimate, and that the lower and upper bounds of the 95% confidence interval for the difference between GSK2982772 60 mg TID (n=18) and placebo (n=6) in percentage change in index lesion PLSS will be within approximately 17.5% of the point estimate.

[figure not shown]

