9.3.2. Interim Analysis

In line with routine pharmacovigilance, an internal GSK Safety Review Team (SRT) which will include members of the GSK2982772 project team, will review blinded safety data, including clinical laboratory parameters and adverse events, at appropriate intervals during the period of study conduct.

In both cohorts, once an appropriate number of subjects randomised to GSK2982772 have completed Day 43 (Week 6), the PLSS data will be reviewed in an unblinded manner by a Data Review Committee (DRC) consisting of the GSK Project Physician Lead (PPL), the study statistician, the study pharmacokineticist, the PRR DPU Head, the Early Development Lead (EDL), the Safety Review Team (SRT) leader, or their designees on an ongoing basis. A physician external to the GSK2982772 project team may also be involved in the data review. Additional inflammatory biomarkers, clinical and mechanistic endpoints (e.g., target engagement) may be reviewed if available. No other member of the GSK core study team will be unblinded to this data. The primary purpose of these reviews will be to monitor PLSS changes for internal decision making purposes. A data review charter will identify the specific GSK individuals involved, outline in detail the activities of this review and how the integrity of the study will be maintained.

A formal interim analysis will be conducted after the completion of Cohort 1 and will only include those subjects randomised to a BID dosing regimen. The purpose of the interim analysis is primarily to provide the project team and key GSK stakeholders with an early indication of the safety and efficacy from the trial, and to facilitate decision making regarding the subsequent clinical development of GSK2982772.

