9.3.4. Secondary Analyses

Comparisons between treatment groups on any changes observed will be conducted for the secondary endpoints if deemed appropriate, e.g. changes in the mean target engagement, changes in inflammatory markers and percentage change in index lesion PLSS be statistically analyzed using a MMRM (repeated measures mixed effects model) comparing each GSK2982772 arm with placebo at each time point. If sufficient numbers of subjects are enrolled with a BSA >5% then the proportion of subjects achieving PASI 50/75/90 at Day 85 (12 Weeks), will be statistically analysed using a Generalised Estimating Equations (GEE) model comparing each GSK2982772 arm with placebo at

each time point if appropriate. Similar analyses will be conducted for other secondary endpoints if deemed appropriate.

The relationship between each of the mechanistic endpoints and also with the clinical endpoints may also be graphically presented and analysed using an appropriate statistical model identifying any trends. The model will determine whether the mechanistic effect significantly explains or predicts the effect on the other mechanistic or clinical endpoints (e.g., index lesion PLSS score). This may be conducted through comparing statistical models incorporating different explanatory terms (i.e. mechanistic endpoints) with the 'null' model (no mechanistic endpoints); or if deemed appropriate, multivariate statistical methods may also be applied to determine the relationship between the key endpoints. The consistency in the changes over time between the endpoints will also be assessed.

In addition, based on the data that we observe in the study, probabilities of success will be determined, where the definition of success will be dependent on the endpoint. For example, what is the probability that we would observe a certain percentage change in PLSS (i.e., comparatory rate), based on the data that we have observed in the study.

GSK2982772 plasma concentrations will be summarised descriptively by Day and nominal time point by dosing regimen.

Further details regarding the statistical analysis will be outlined in the Reporting and Analysis Plan (RAP).

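### BID and TID appear set to share one pooled placebo arm although placebo is randomised separately in each cohort, so a difference between cohorts would shift both effects, TID more

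*Protocol*

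**What the plan says.** Section 9.1 (Hypotheses) provides that, if appropriate, "comparisons between the GSK2982772 arms and the placebo arm will be made" for the secondary objectives: several active arms, one placebo arm. Section 9.3.4 (Secondary Analyses) plans a repeated measures mixed model for percentage change in index lesion PLSS and other endpoints, "comparing each GSK2982772 arm with placebo at each time point". It names no cohort term and does not say which placebo subjects enter which contrast. Further detail is left to the Reporting and Analysis Plan.

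Randomisation is within cohort. Section 6.2 gives a 2:1 ratio for Cohort 1, dosed twice daily. For Cohort 2, dosed three times daily, it says: "Subjects will be randomised to receive either GSK2982772 or placebo in a 3:1 ratio". Section 9.2.1 gives the sizes: "In Cohort 1, approximately 30 subjects and up to a maximum of 36, will be randomised into the study" and "In Cohort 2, approximately 24 subjects and up to a maximum of 32, will be randomised into the study". At the planned sizes that is 20 BID and 10 placebo, then 18 TID and 6 placebo. No subject can appear in both cohorts (Section 5.2, criterion 20): "Subjects who were randomized into Cohort 1 are not eligible to be re-randomized into Cohort 2".

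Section 9.2.1 also gives the expected precision for PLSS at a standard deviation of 25%. The 95% limits lie within about 17.1% of the estimate for BID (n=20) against placebo (n=10), and within about 17.5% for TID (n=18) against placebo (n=6).

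Section 9.3.2 adds an interim: "A formal interim analysis will be conducted after the completion of Cohort 1", which "will only include those subjects randomised to a BID dosing regimen".

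**The concern.** A placebo subject protects a treatment comparison from bias only if that subject could have been allocated to the treatment in question. With one pooled placebo arm, 10 of the 16 placebo subjects set against TID were never randomised against TID, and 6 of the 16 set against BID were randomised in the other cohort. Each comparison is then only partly randomised.

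The protocol itself shows how the cohorts differ. Cohort 2 was added by Amendment 2, so calendar time may differ. The chance of active treatment is 2 in 3 in one cohort and 3 in 4 in the other. The tablet schedule is twice daily in one and three times daily in the other. Section 4.4 justifies a placebo group because autoimmune disease fluctuates naturally, which is also a reason to prefer placebo subjects from the same cohort.

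If mean outcome differs between cohorts for such reasons, part of that difference passes into the estimated regimen effects, and it could imitate or hide an effect of TID. Pooling would also move the BID estimate between the interim (10 placebo subjects) and the final analysis (16) without any new BID subject.

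**Working it through.** **Inputs.** From Section 9.2.1: SD 25 points; 20 BID and 10 placebo; 18 TID and 6 placebo; 95% two-sided intervals. The cohort shift d (Cohort 2 minus Cohort 1, in points of percentage change in PLSS) is not in the protocol and is assumed.

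**Step 1: the protocol's own half-widths.** Half-width = t(0.975, n1+n2−2) × 25 × √(1/n1 + 1/n2).

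| Comparison | SE | t | Half-width | Stated |
|---|---|---|---|---|
| BID 20 v 10, as labelled | 9.68 | 2.048 | 19.8 | 17.1 |
| TID 18 v 6, as labelled | 11.79 | 2.074 | 24.4 | 17.5 |
| BID 20 v 16, pooled | 8.39 | 2.032 | 17.04 | 17.1 |
| TID 18 v 16, pooled | 8.59 | 2.037 | 17.50 | 17.5 |

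A normal quantile does not rescue the labelled sizes (19.0 and 23.1), nor does a common residual of 50 degrees of freedom (19.5 and 23.7). With 10+6 = 16 placebo subjects, TID matches exactly and BID to within 0.06. The figures were therefore worked out with a shared placebo arm.

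**Step 2: bias from pooling without a cohort term.** The pooled placebo mean contains 6/16 of d.

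- BID subjects carry none of d, so the BID effect is shifted by 0 − (6/16)d = −0.375d.
- TID subjects carry all of d, so the TID effect is shifted by d − (6/16)d = +0.625d.

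Least squares on the 54 planned subjects, with no true effect and d = 10, returns −3.75 and +6.25 without a cohort term, and 0 and 0 with one. At maximum enrolment (placebo 12 and 8) the factors become −0.40 and +0.60.

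**Step 3: effect on the interval.** Non-coverage = P(|Z + bias/SE| > 1.96), with SE 8.39 for BID and 8.59 for TID.

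| Assumed d | BID bias | BID non-coverage | TID bias | TID non-coverage |
|---|---|---|---|---|
| 5 | −1.9 | 5.6% | +3.1 | 6.5% |
| 10 | −3.75 | 7.3% | +6.25 | 11.2% |
| 15 | −5.6 | 10.3% | +9.4 | 19.4% |

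**Step 4: can the trial detect such a shift?** The SE of the placebo difference between cohorts is 25 × √(1/10 + 1/6) = 12.9 points, so a shift of 10 or 15 points could easily pass unnoticed.

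**Step 5: what pooling buys.** Pooling has the smaller mean squared error while weight × |d| is below √(within-cohort variance − pooled variance).

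- BID: √(93.75 − 70.31)/0.375 = 12.9 points.
- TID: √(138.89 − 73.78)/0.625 = 12.9 points.

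**The case against.** The strongest reply is that the protocol does not fix a pooled analysis. The comparisons are made only if appropriate, the model detail goes to the Reporting and Analysis Plan, and a cohort term there would not contradict Section 9.3.4. The singular placebo arm in Section 9.1 is weak evidence, since the arm wording there is loose: the next sentence speaks of both treatment arms. The n=10 and n=6 labels in Section 9.2.1 even point to within-cohort contrasts. Much of this stands, and the missing cohort term is no fault by itself. What remains is that the stated comparator and the stated precision both rest on a shared placebo arm. If the analysis plan does separate the cohorts, the half-widths in Section 9.2.1 are too small.

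Second, pooling is a legitimate choice. Below a shift of about 12.9 points it has the smaller mean squared error, and d = 10 falls in that range. The within-cohort TID estimate rests on 6 placebo subjects, with a half-width of 24.4, nearly one SD. This stands, and it is why the point does not ask that the within-cohort estimate must lead.

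Third, the interim on Cohort 1 would use only BID subjects and their own placebo group. This stands for BID at that stage. It gives nothing comparable for TID and leaves the final BID analysis open.

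Some stronger readings go too far:

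- A reader might infer that a shift exists. No document shows one, and the values of d are assumptions.
- A reader might suspect different sites or a different case mix. The protocol gives no support for this: Sections 5.1 and 5.2 apply the same criteria to both cohorts.
- A reader might take Cohort 2 to exist in order to show that TID adds efficacy over BID. Section 4.5 and the Amendment 2 rationale speak of trough exposure and of simulating a modified-release profile, and neither Section 9.1 nor 9.3.4 states a TID-versus-BID contrast.

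**Conclusion.** The point holds as a matter of an unstated assumption and incomplete reporting. Section 9.1 and the arithmetic behind Section 9.2.1 indicate one placebo arm of 16 for both regimens, while randomisation is separate by cohort and the labels say 10 and 6. Under pooling without a cohort term, a cohort shift of d moves the BID effect by −0.375d and the TID effect by +0.625d. At assumed shifts of 5 to 15 points, non-coverage is about 5.6% to 10.3% for BID and 6.5% to 19.4% for TID, against a nominal 5%.

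These figures assume an additive shift, SD 25, full planned numbers, one time point and a normal approximation. They do not show that the trial's estimates are biased or that pooling is wrong. The comparisons are secondary, the study is not powered for differences, and the primary safety review is descriptive and unaffected.

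**What to change.** In Section 9.3.4, state which placebo subjects serve each contrast. Report, for BID and for TID, the within-cohort estimate against concurrent placebo from a mixed model with cohort and cohort-by-visit terms, beside the pooled-placebo estimate, and show placebo means by cohort. Which of the two leads is the sponsor's choice and should be stated. In Sections 9.1 and 9.2.1, say that the pooled estimate assumes no shift between cohorts, and that 17.1% and 17.5% rest on 16 placebo subjects.

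The cost is some wording and one more model run; no new subjects or data are needed, and the pooled result loses no precision. The downside is wider within-cohort intervals: at SD 25, about 19.8 for BID against 17.0 pooled, and 24.4 for TID against 17.5 pooled.
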